## 6. STUDY PROCEDURES/EVALUATIONS AND SCHEDULE

### 6.1 STUDY SPECIFIC PROCEDURES

#### 6.1.1 MEDICAL HISTORY

A medical history will be obtained by the investigator or qualified designee. In addition to collecting information on demographics, the medical history will include all active conditions, and any prior conditions that are considered to be clinically significant by the PI. Details regarding the participant's cancer will be recorded separately and not listed as medical history.

#### 6.1.2 DISEASE ASSESSMENT

The investigator or qualified designee will obtain prior and current details regarding the participant's cancer.

#### 6.1.3 MEDICATION HISTORY

A complete medication history will be acquired concurrent with medical history. Concomitant prescription, over-the-counter medications and any supplements or herbals should be captured prior to start of SBRT.

#### 6.1.4 PHYSICAL EXAMINATION

Physical exams must be performed by a medically qualified individual such as a licensed physician, Physician's Assistant or advanced Registered Nurse Practitioner as local law permits and per institutional standards. The physical examination to be conducted will include an evaluation of: general appearance; head, ears, eyes, nose, and throat; neck; skin; cardiovascular system; respiratory system; gastrointestinal system; lymphatic system, musculoskeletal system, and nervous system. All other physical exams after baseline will include an evaluation of any AEs, or any previously reported symptoms, or prior physical examination findings. All physical examinations will also include:

##### 6.1.4.1 Vital signs

Vitals to be collected include BP, HR, temperature, and oxygen saturation by pulse oximetry. As part of screening/baseline visit, vitals should be obtained within 14 days prior to first dose of SBRT. Vitals will also be obtained during treatment.

Significant findings that were present prior to the signing of the informed consent must be included in the Medical History CRF. Significant new findings that begin or worsen after informed consent must be recorded on the Adverse Event CRF.

##### 6.1.4.2 Height and weight

Height, weight, body surface, will be collected at initial radiation oncology consultation.

##### 6.1.4.3 Performance status

Performance status will be determined for all participants at screening and at select times during treatment as per assessment schedule in Section 6.8. Refer to Appendix B for performance criteria.

#### 6.1.5 RADIOGRAPHIC OR OTHER IMAGING ASSESSMENTS

All imaging for radiation planning and subsequent follow-up will be in accordance with institutional standards, and include (but are not limited to): multiphasic CT (4D-CT), CT, MRI, X-ray, Fluorodeoxyglucose (FDG) Positron emission tomography (PET), and ultrasound. Cone-beam CT will be obtained prior to each fraction delivered. Imaging procedures will occur according to Section 6.8, Schedule of Events, but may occur more frequently if clinically indicated.

#### 6.1.6 ADVERSE EVENT EVALUATION

Toxicities and adverse experiences will be assessed at each visit using the [CTCAE v5.0](#) and quantifying current Child-Pugh score to assess risk of RILD. Adverse events will be monitored from the time the participant signs the Consent Form up until 3 months following SBRT. Participants will be instructed to report all AEs during the study and will be assessed for the occurrence of AEs up until 3 months following radiation therapy. All AEs (serious and non-serious) must be recorded on the source documents and CRFs regardless of the assumption of a causal relationship with the study therapy.

For details on AE collection and reporting, refer to Section 8.6.

##### 6.1.6.1 Radiation-induced liver toxicity

Radiation-induced liver disease (RILD) is defined as either classical or non-classical RILD. Classical RILD (typically occurring in patients without background liver dysfunction or cirrhosis) is characterized as the presence of nonmalignant ascites and anicteric elevation of alkaline phosphatase level twice the upper level of normal or baseline value occurring between 2 weeks and 3 months after the completion of irradiation. Non-classical RILD (typically occurring in patients with baseline liver dysfunction or cirrhosis), occurs is defined as grade 4 AST and/or ALT elevations, or an increase in CP score of  $\geq 2$  within 1 week to 3 months after completing SBRT.

#### 6.1.7 FIDUCIAL MARKER PLACEMENT

The type of fiducial along with method implantation will be according to institutional standards and at the discretion of the treating radiation oncologist, as some tumors may be targetable without fiducial guidance. Participants should discontinue antiplatelet medications approximately 7 days before the fiducial implantation. In general, warfarin should be discontinued 5 days before insertion, and heparin and related products discontinued approximately 12-24 hours prior to the procedure. Absent any complications, these treatments may be approximately restarted 24-48 hours following the procedure.

#### 6.1.8 ASSESSMENT OF PARTICIPANT-REPORTED OUTCOMES

Quality of life (QoL) care metrics using the will be assessed using the EORTC QLQ-C30 and FACT-Hep questionnaires at time points shown in Section 6.8, Schedule of Events. The questionnaire will each take <45 minutes to complete.

## 6.2 LABORATORY PROCEDURES AND EVALUATIONS

### 6.2.1 HEMATOLOGY

Hematologic profiling will be collected per institutional standards, and should include evaluation of hematocrit, hemoglobin, platelets, white blood cells with differential (basophils, eosinophils, lymphocytes, monocytes, neutrophils), and absolute lymphocyte count.

### 6.2.2 BIOCHEMISTRY

Blood chemistry will be collected per institutional standards and should include the following: Liver function test (LFT), including: Total Protein, Albumin, Total Bilirubin, Alkaline Phosphatase, AST, ALT serum creatinine, blood urea nitrogen, calcium, potassium, and alpha-fetoprotein tumor marker (AFP).

### 6.2.3 COAGULATION PANEL

INR will be collected for calculation of CP score

### 6.2.4 ECHOCARDIOGRAM

As clinically indicated.

### 6.2.5 PREGNANCY TEST

A serum or urine pregnancy test is required during screening for all persons of childbearing potential. The pregnancy test is required within 72 hours prior to study intervention and results must be available prior to administration of SBRT. If the urine pregnancy test is positive, a serum pregnancy test must be performed per institutional standards.

## 6.3 SCREENING ASSESSMENTS

A screening (consultation) visit may occur as part of standard of care. If a participant is eligible for the study after review of key inclusion/exclusion criteria, additional screening visits will be scheduled while staff members are requesting insurance authorization to participate in a clinical trial.

The following will be reviewed at screening visit:

- Clinical history and physical exam (per standard of care)
- Informed consent obtained and documented

Toxicities which occur prior to the start of treatment will not be subject to analysis. Consent must be obtained before initiation of any clinical screening procedure that is performed solely for the purpose of determining eligibility for this research study. Evaluations performed as part of routine care before informed consent can be utilized as screening evaluations if done within the defined time period.

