### 4.2 PARTICIPANT EXCLUSION CRITERIA

An individual who meets any of the following criteria will be excluded from participation in this study:

1. Participants have any one of the following liver tumor characteristics:
  - a. have  $> 5$  liver tumors, or
  - b. maximal diameter  $> 5$  cm
2. Complete obstruction of portal venous flow to the segment of liver that includes the target lesion
3. Prior radiotherapy to the upper abdomen or radioembolization of the liver, or prior thermal

ablation to the target lesion.

4. For fiducial marker placement:
  - a. Have a gold allergy,
  - b. Any coagulopathy preventing safe fiducial placement
5. Contraindication to both contrast enhanced MRI and contrast enhanced CT (i.e. unable to undergo follow-up imaging or SBRT treatment planning)
6. Participation in another concurrent treatment protocol
7. Participant is pregnant or breastfeeding, or expecting to conceive or father children within the projected duration of the trial, starting with the screening visit through 120 days after the last dose of trial treatment.
8. Uncontrolled intercurrent illness, including but not limited to, ongoing or active infection, symptomatic congestive heart failure, uncontrolled hypertension, unstable angina pectoris, cardiac arrhythmia, interstitial lung disease, serious chronic gastrointestinal conditions associated with diarrhea, or psychiatric illness/social situations that would limit compliance with study requirement, substantially increase risk of incurring AEs or compromise the ability of the patient to give written informed consent

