## 4.5 PARTICIPANT SCREENING AND ENROLLMENT

In order to participate in this study, signed informed consent must be obtained from the participant or the participant's legally acceptable representative. The current Institutional Review Board (IRB) approved informed consent must be signed and dated by each participant prior to undergoing any study procedures or before any prohibited medications are withheld from the participant in order to participate in this study.

Screening will begin once the participant has provided written informed consent to participate in the study and ends on Day 1 of the study. All screening and baseline evaluations will be performed during the screening phase (i.e., up to 28 days before on-study treatment is initiated). Day 1 of the clinical trial will be when participants are administered first dose of SBRT. Total accrual of all participants is anticipated to take a total of 12 month.

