#### 5.1.1 SIMULATION

All imaging for radiation planning will be performed according to institutional guidelines. If deemed necessary by the treating radiation oncologist for targeting purposes, eligible participants will undergo placement of intrahepatic fiducial markers prior to simulation (refer to Section 6.1.7). Imaging for radiation planning will include triple-phase contrast-enhanced simulation with immobilization. Participants will be immobilized with standard motion management techniques. The simulation should be performed with the participant in treatment position (i.e., supine, with arms above head).

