## 6.8 SCHEDULE OF EVENTS

Visit Days	Screening	Treatment					Follow-Up B (±4 weeks)	
	Days -28 to -1	Days † (+7 days)						
		1	3	5	7	9*		
SBRT A		X	X	X	X	X		
Informed consent	X							
Inclusion/exclusion criteria	X							
Medical history	X						X B	
Prior/concomitant medications	X						X B	
Physical Examination C	X						X B	
Radiographic Imaging	X	X D	X D	X D	X D	X D	X E	
Hematology F	X						X B	
Biochemistry G	X						X B	
Coagulation	X						X	
Pregnancy test	X							
Fiducial placement (if needed)	X							
AE assessment	X	X					X	
EORTC QLQ-30	X						X B	
FACT-Hep	X						X B	

† Starting on day 1, SBRT dose fractions are given every other day (i.e., Monday-Friday), but not administered on Saturdays, Sundays, or holidays. Dosing interruptions because of weekends and holidays will be recorded in CRF.

\*Day 9 study assessments of radiographic imaging and AE collection will serve as Early Termination and/or End of Treatment Visit.

A Scheduled SBRT visits may be delayed by no more than 7 days between each visit, or may occur earlier than scheduled by no more than 3 days.

B Follow-up assessment to occur 6 weeks following completion of SBRT then every 3 months up to 2 years post SBRT therapy

C All physical exams will include assessing weight, vital signs, and ECOG performance status. Height will be measured at screening visit only.

DCone-beam CT will be obtained prior to each SBRT fraction.

E Participants will undergo surveillance imaging (e.g., CT scan) 6 weeks following completion of SBRT and then every 3 months for the first 2 years.

F Hemoglobin, platelets and white cell count with differential white count

G Biochemistry to include renal (creatinine, urea, sodium, potassium) and liver function (AST, ALT, bilirubin)

HAEs and laboratory safety measurements will be graded per NCI CTCAE version 5.0 as well as definition of radiation-induced liver disease (Child-Pugh elevation of 2 or more). All AEs, whether gradable by CTCAE or not, will also be evaluated for seriousness. Record all AEs and SAEs occurring from the time of consent signing to 3 months following the completion of SBRT.

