### 8.7 STUDY STOPPING RULES

The overall study will be paused, and appropriate authorities (e.g., IRB, Knight Data and Safety Monitoring Committee) notified if the following events occur:

- Life-threatening grade 4 toxicity attributable to protocol therapy that is unmanageable, or unexpected
- Death suspected to be related to SBRT

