### 9.1 ANALYSIS POPULATIONS

Safety analysis set: All participants will be evaluable for toxicity from the time of their first fraction of SBRT.

Efficacy analysis set: The analysis population to assess transplantation eligibility (i.e., Milan criteria) and efficacy endpoints (e.g., localized control rate, intrahepatic progression, extrahepatic progression and overall survival), will include only participants who have received at least 85% of the prescribed SBRT dose (i.e., 85% Level 0 = 34 Gy; 85% Level -1 = 30 Gy; 85% Level -2 = 25.5 Gy).

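### Adverse events from fiducial placement are recorded but barred from analysis if they start before the first SBRT fraction, so the pilot will not report harm from an invasive step used to deliver SBRT

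*Combined protocol and SAP*

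**What the plan says.** **Placement.** Section 5.1.1 states that, where needed for targeting, "eligible participants will undergo placement of intrahepatic fiducial markers prior to simulation". The schedule in 6.8 lists placement in the screening column, Days -28 to -1. Section 6.1.7 leaves the decision to the treating radiation oncologist, accepts that some tumours can be targeted without markers, and asks for antiplatelets, warfarin and heparin to be held beforehand. Section 4.2 excludes patients with "Any coagulopathy preventing safe fiducial placement".

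**Start of treatment.** Section 4.5 starts screening at consent and adds: "Day 1 of the clinical trial will be when participants are administered first dose of SBRT".

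**Collection.** Section 6.1.6 states: "Adverse events will be monitored from the time the participant signs the Consent Form up until 3 months following SBRT". All events are to be recorded whatever their cause. Section 8.5 and the schedule's adverse-event footnote give the same window.

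**Analysis.** Section 6.3: "Toxicities which occur prior to the start of treatment will not be subject to analysis". Section 9.1, safety set: "All participants will be evaluable for toxicity from the time of their first fraction of SBRT".

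**Screen failures.** Under 6.3.1, anyone who consents but does not start SBRT is a screen failure. Only the demographic, consent and eligibility pages and the reason for failure go into the database.

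**The concern.** Placement is an invasive liver procedure done only so that SBRT can be delivered. The protocol itself treats it as carrying bleeding risk: it excludes unsafe coagulopathy and interrupts drugs that affect clotting. The population has Child-Pugh B8 or worse cirrhosis. A bleed at placement, or a clot while anticoagulation is held, is a cost of the treatment pathway even though no radiation has yet been given.

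Section 9.3.1 gives the main purpose of the pilot as finding unforeseen problems before a larger trial, and section 1.3 adds identifying barriers to participation. Under the analysis rules, a participant could have a serious complication of placement, recover, be irradiated, and appear in the safety results without that event. The planners of the next trial would not see it in the report.

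**Working it through.** The point rests on reading the sections against each other. Arithmetic enters only at the end.

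**1. Order of events for a treated participant who has markers.** Consent; any drug interruption; placement; simulation; planning; first fraction (Day 1). Placement lies after consent (4.5, 6.8) and before Day 1 (5.1.1, 6.8).

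**2. Rules applied to an event that starts between placement and Day 1.**

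| Rule | Section | Result |
|---|---|---|
| Recorded on the case report form? | 6.1.6, 6.8, 8.5 | Yes, from consent |
| Treated as baseline? | 8.5 | No. Only conditions present at screening are baseline; later deterioration is an adverse event |
| Analysed? | 6.3 | No, onset is before treatment |
| In the safety set's time window? | 9.1 | No, the window opens at the first fraction |
| Visible to the monitoring committee? | 10.1 | Possibly; adverse events, serious events and deaths may be supplied |

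Nothing elsewhere in the plan brings the event back into the reported results.

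**3. Would a named safety estimate capture it otherwise?** Section 9.2.3 names non-classic radiation-induced liver disease, a Child-Pugh rise of 2 or more, and CTCAE liver toxicity. The synopsis limits the first and third to the period from 1 week to 3 months after SBRT. A procedural bleed is in none of these as such, so deleting the 6.3 sentence alone would not get it reported. A separate table is needed.

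**4. Participants who have markers and are never irradiated.** Markers are placed before simulation, whereas the dose constraints can be checked only on a plan made after it. Section 9.3.1 predicts that 20% of plans will fail.
- The plan's own sample size reproduces: ln(0.05)/ln(0.80) = 13.43, rounded up to 14. At the stated 15, the chance of at least one failure is 1 − 0.80^15 = 0.965.
- Expected plan failures: 0.20 × 15 = 3 if 15 are planned. If 15 are to be treated, 15/0.80 = 18.75, so about 19 consent and about 4 are not treated.

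The documents do not say how many of these would already have markers. For any who do, 6.3.1 keeps their adverse events out of the database, which conflicts with recording every event from consent.

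**5. Size.** One event among 15 treated participants is 1/15 = 6.7%. With only those who had placement as denominator, the percentage for one event is the same or higher.

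**The case against.** Counting toxicity from first treatment is a common convention, and 6.3 and 9.1 agree with each other. That is fair, and the point does not ask for SBRT toxicity to be counted from any other date. The convention still leaves harm from a preparatory procedure with no place in the report.

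Several stronger readings are tempting, and the documents do not support them:

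- *That the reported liver toxicity is biased low.* Step 3 shows that a procedural bleed is not a component of any named estimate. Lasting decompensation after placement might raise or lower the observed Child-Pugh change, depending on whether baseline was scored before or after placement. The plan does not fix that date, so no direction of bias can be shown.
- *That such an event becomes baseline.* Section 8.5 makes it an adverse event.
- *That complications never count.* One that starts after the first fraction falls in the safety set's window.
- *That every participant is exposed, or that the patients are coagulopathic.* Placement is optional, drug interruption affects only those taking the drugs, and unsafe coagulopathy is excluded. A score of B8 is possible with INR at 1 point: albumin, ascites and bilirubin at 2 each, INR and encephalopathy at 1 each, total 8.
- *That a death from placement would go unexamined.* The second trigger in 8.7 reads "Death suspected to be related to SBRT", but the first refers to protocol therapy, 4.8 allows suspension for adverse events in general, and the monitoring committee may see deaths on study. Whether 8.7 covers placement is unclear; the text does not settle it either way.

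It is also true that no primary or secondary estimate changes, and that this is a 15-patient pilot without a hypothesis test. That limits the weight of the point but does not remove it.

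**Conclusion.** The point holds as a reporting gap. An explicit rule excludes from the safety results data that the protocol collects on complications of marker placement and the associated drug interruption, when onset precedes the first fraction. For participants who have placement and then fail screening, the data are not entered at all. This runs against the pilot's stated purpose.

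The documents give neither the share of participants needing markers nor a complication rate. If, purely as an assumption, 25% to 100% need markers and 2% to 10% of placements cause a complication, the expected number among 15 runs from 15 × 0.25 × 0.02 = 0.075 to 15 × 1.00 × 0.10 = 1.5. That range is too wide to rest anything on, and the conclusion does not depend on it. The only size claimed is 6.7% of 15 per event. This is a modest but cheap improvement.

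**What to change.** 1. Amend the 6.3 sentence and section 9.1 so that adverse events from the start of marker placement, including the associated drug interruption, up to the first fraction are tabulated descriptively and separately as procedure-related. The denominator is the number of participants who had placement. SBRT toxicity continues to be analysed from the first fraction.
2. Reconcile 6.3.1 with 6.1.6 and 6.8 so that adverse events in participants who had placement and then failed screening are entered and appear in that table.
3. The sponsor should reconcile the terms in 8.7 and state whether protocol therapy and SBRT, as used there, include marker placement.

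Cost: a protocol wording change, one extra table and a little added data entry. For treated participants the data are already collected; for screen failures who had placement they are not, and entry must be added. The reported safety profile may look slightly less favourable.

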### 6.3.1 SCREEN FAILURES

A participant who signed an informed consent form but does not initiate planned SBRT, for any reason, will be considered a screen failure. Those found not to be eligible after signing the study consent will be considered screening failures, and data will be handled in the same manner. The demographic information, informed consent, and inclusion/exclusion pages must also be completed for screen failures. No other data except reason for screen failure will be entered into the clinical database for individuals who are screen failures.

#### **6.4 ASSESSMENTS DURING TREATMENT**

Participants will be assessed once during the course of 5 fraction SBRT. Specific on-study assessments are listed in the Section 6.8, Schedule of Events. Under certain circumstances (e.g., clinic holiday, inclement weather) scheduled visits may be delayed by no more than 7 days between each visit.

#### **6.5 FOLLOW-UP**

Participants will be followed and disease assessments will take place 6 weeks following completion of SBRT, then every 3 months up until enrollment on hospice or death, or 2 years from time of last SBRT dose, whichever occurs first. Follow-up visits will be consistent with standard of care, and assessments are listed in Section 6.8. Any participants removed from protocol therapy for unacceptable AE(s) will be followed until resolution or stabilization of the AE.

#### **6.6 EARLY TERMINATION OR END OF TREATMENT VISIT**

Any participant that discontinues treatment earlier than planned must be evaluated within 30 days after termination or prior to the initiation of any other off-study interventional therapy, if not performed within the last 30 days. On-treatment Day 9 study visit and associated assessments (i.e., radiographic imaging and AE assessments) will serve as the end of treatment visit (Section 6.8, Schedule of Events). These assessments also pertain to participants that discontinue study intervention.

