#### 5.2 DOSING DELAYS AND MODIFICATIONS

SBRT will be delivered in a total of 5 fractions over two weeks, with treatments delivered every other day between Monday and Friday. SBRT will not occur on Saturdays, Sundays or holidays. There should be no more than a 14 day interruption between the planned administration of each fraction. Dosing interruptions lasting longer than 14 days between each fraction, for any reason, are considered an unacceptable and participants will be removed from

study and replaced with another participant. Participants removed from study will be treated per institutional standards or offered participation in another clinical trial if one is available. All dosing interruptions should be recorded in CRF.

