#### 9.2.3 ANALYSIS OF THE SECONDARY ENDPOINTS

Using the efficacy analysis set, the estimate of local control rate, intrahepatic progression free survival, and overall survival, will be plotted using Kaplan-Meier curve and reported with median survival and 95% CI if available. Using the same efficacy analysis set, the proportion of participants that proceed to transplantation, will be measured and reported with 95% CI.

Non-classic RILD, liver toxicity defined as a  $\geq 2$  increase in CP score (**Appendix A**), and liver toxicity per CTCAE v5.0, will be estimated along with an exact CI using the safety analysis set.

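### The bloods behind the required Child-Pugh score are not scheduled at the early-termination visit, and participants removed under Section 5.2 stay in the RILD analysis set with no later liver tests scheduled

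*Combined protocol and SAP*

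**What the plan says.** **Early-termination visit.** Under Section 6.6, anyone who stops SBRT early "must be evaluated within 30 days after termination", or before other therapy starts, unless already evaluated in the preceding 30 days. The content is set as follows: "On-treatment Day 9 study visit and associated assessments (i.e., radiographic imaging and AE assessments) will serve as the end of treatment visit", and "These assessments also pertain to participants that discontinue study intervention". Section 4.6 sends everyone who discontinues treatment, other than by withdrawing consent, to this visit. In Section 6.8, hematology, biochemistry and coagulation are marked at screening and follow-up but on no treatment day.

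**Child-Pugh.** Section 6.1.6 asks for the current Child-Pugh score as part of the toxicity assessment at each visit. Appendix A builds the score from albumin, bilirubin, INR, ascites and encephalopathy. Section 6.2.3 says INR is collected for this purpose.

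**Removal.** Section 5.2: "Dosing interruptions lasting longer than 14 days between each fraction, for any reason" lead to the participant being taken off the study and replaced. Afterwards they receive institutional treatment or may be offered another trial.

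**RILD.** Section 6.1.6.1 defines the non-classic form as grade 4 AST or ALT, or "an increase in CP score of" 2 or more, from 1 week to 3 months after SBRT is completed. Section 9.2.3 says it "will be estimated along with an exact CI using the safety analysis set", and Section 9.1 defines that set: "All participants will be evaluable for toxicity from the time of their first fraction of SBRT".

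**Missing data.** Section 9.4 rules out imputation, allows a participant with insufficient data to be left out of an endpoint, and requires the analysed number and the reasons for exclusion to be stated.

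**The concern.** Neither limb of the RILD definition can be fully assessed without bloods. A participant who stops SBRT early has none scheduled at the termination visit. If the stop is a gap of more than 14 days, the participant also leaves the study and its follow-up visits. Yet one fraction is enough to place that participant in the set on which RILD is estimated.

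Interruptions may be caused by worsening liver function in a population enrolled at Child-Pugh B8 or higher. Where they are, the missing scores belong to people with a raised chance of RILD. The plan would then lose safety information in the patients about whom the pilot most needs it, and the reported rate would be too low for planning the larger trial mentioned in Section 1.3.

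**Working it through.** The plan gives no early-stopping rate and no precision target for RILD, so there is no stated figure to reproduce. Its sample-size figure does not bear on this point. The check sets the sections together and then sizes the effect under stated assumptions.

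1. **Who is affected.** Taking the five fractions as equal, four of five is 4/5 = 80% of the dose: 32, 28 or 24 Gy against the Section 9.1 thresholds of 34, 30 and 25.5 Gy. Anyone who misses a fraction therefore leaves the efficacy set but stays in the safety set, where RILD is estimated.

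2. **When bloods are scheduled.** The RILD window is week 1 to about week 13. The 6-week visit with its ±4-week allowance falls at weeks 6 − 4 = 2 to 6 + 4 = 10, inside the window. If the next visit is 3 months after that one, it falls at about 6 + 13 − 4 = 15 to 6 + 13 + 4 = 23, outside it. If it is instead counted 3 months from the end of SBRT, it falls at about weeks 13 − 4 = 9 to 13 + 4 = 17, straddling the end. On the first reading a single laboratory visit supplies the RILD score, and a participant removed before it has none scheduled.

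3. **Time origin.** The RILD definition and the 6-week visit (Sections 6.5 and 6.8) both count from completion of SBRT, an event a non-completer does not have.

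4. **Direction of bias.** Let n be the number in the safety set, u of them unscored, with RILD risk r_s in the scored and r_u in the unscored. The true proportion is [(n − u)·r_s + u·r_u]/n.
   - Unscored kept as non-events: bias = −(u/n)·r_u. This is low whenever r_u is above zero.
   - Unscored excluded: bias = −(u/n)·(r_u − r_s). This is low whenever r_u exceeds r_s, as it would if stopping is liver-related, and zero if the risks are equal.

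5. **Size.** Assumptions: n = 15, 3 observed events, u = 2. Exact (Clopper–Pearson) limits for x of m are the 2.5% point of Beta(x, m − x + 1) and the 97.5% point of Beta(x + 1, m − x).

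| Handling of the 2 unscored | Proportion | 95% CI |
|---|---|---|
| Kept as non-events | 3/15 = 20.0% | 4.3–48.1% |
| Excluded | 3/13 = 23.1% | 5.0–53.8% |
| Both true events | 5/15 = 33.3% | 11.8–61.6% |

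   If both had RILD, the shortfall is 33.3 − 20.0 = 13.3 points when they are kept and 33.3 − 23.1, about 10.3 points before rounding, when they are excluded.

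6. **Sensitivity.** With 1 to 3 unscored and 3 observed events, the proportion is 20.0% throughout if they are kept, 21.4% to 25.0% if excluded, and 26.7% to 40.0% if all were events. With 4 observed and 2 unscored, the extremes are 4/15 = 26.7% and 6/15 = 40.0%. If the 2 are replaced so that 15 are scored, the figures are 3/17 = 17.6% (3.8–43.4%) kept, 3/15 = 20.0% excluded, and 5/17 = 29.4% (10.3–56.0%) if both were events.

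**The case against.** Several stronger readings are tempting, and the documents do not support them.

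- **That the plan wants no Child-Pugh score from early stoppers.** Section 6.1.6 asks for one at each visit, and an adverse-event assessment is part of the termination visit. The defect is a conflict between 6.1.6 and 6.6/6.8: a score is required and its bloods are not scheduled.
- **That everyone who stops early is lost.** Removal from study is stated for gaps over 14 days. Section 4.6 honours continued follow-up where possible. Section 6.5 follows those taken off therapy for unacceptable adverse events until resolution or stabilization, Section 8.5 follows events similarly, and Section 6.7 records unscheduled laboratory results. Such participants may reach the 6-week bloods. What stands is that none of these sections names the tests, and none says whether it reaches someone removed under 5.2.
- **That unscored people are counted as free of RILD.** Sections 9.1 and 9.2.3 give no such rule, and 9.4 permits exclusion. Dilution through replacement likewise arises only if unscored people are kept as non-events. Exclusion does not remove the bias when stopping is liver-related.
- **That a positioning scan is required of people no longer treated.** Section 6.8 says "Cone-beam CT will be obtained prior to each SBRT fraction", so with no fraction none is called for.
- **That this undermines the trial's main safety result.** RILD is one of several secondary endpoints, and no hypothesis is formally tested.

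On timing, the end column in Section 3.2.2 already runs to 3 months after the last SBRT dose, which a non-completer does have. The definition in the same row and in 6.1.6.1 still counts from completion, so the two need aligning.

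It is also fair to say that the affected group may be empty, that the worst case assumes every unscored person had RILD, and that the intervals overlap heavily. Scores taken after removal could reflect another therapy. These limit the size of the problem but do not settle how a treated participant without a score should be handled.

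**Conclusion.** The point holds in a limited form. The termination visit does not schedule the bloods that Section 6.1.6 presupposes, and the time origin for RILD and the 6-week visit is unclear for non-completers. The clear loss of data is in participants removed under Section 5.2, who remain in the safety set with no later liver tests scheduled.

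In the illustration, a reported 20.0% or 23.1% could stand for a true 33.3%. The reported figure would sit within the 20–30% range quoted in Section 8.4.1 while the true one lay above it. This rests on an assumed 2 unscored participants of 15, both with RILD. If stopping is unrelated to the liver, exclusion under 9.4 costs precision but introduces no bias. The primary endpoint is not affected by the RILD scoring gap.

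**What to change.** 1. In Sections 6.6 and 6.8, add the Section 6.2.2 biochemistry, INR and a Child-Pugh score to the early-termination visit, in line with 6.1.6. Include albumin, which 6.2.2 lists and footnote G of 6.8 omits.
2. In Section 5.2, separate stopping protocol treatment from leaving the study. Anyone with at least one fraction who has not withdrawn consent keeps the Section 6.8 follow-up laboratory visit or visits through 3 months. The 14-day treatment rule itself is left as it is. This step is needed as well as the first, because the termination visit can fall before the RILD window opens.
3. Time the RILD window (Sections 3.2.2 and 6.1.6.1) and the 6-week visit (Sections 6.5 and 6.8) from the last fraction received.
4. In Section 9.2.3, report RILD with the number unscored, and give the range from counting all of them as non-events to counting all as events.

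The cost is amendment wording and a few routine blood draws. The reported RILD rate may be higher, and some scores will follow other therapy and should be flagged as such.
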